^{25, 26}. CD8 regulatory/suppressor cell function is slightly reduced in stable MS, very low during attacks and progression, and rebounds during recovery ²⁵. The defect is localized to the CD8+CD28- population ^{22, 27, 28}, a better marker than FOXP3 in this subpopulation ²⁶. We have found that CD8+CD28-Treg cells are very low in therapy-naive MS compared to healthy controls. Some MS immune modulators can elevate numbers of this subpopulation, and thus enhance anti-inflammatory functions and reduce inflammatory Th1/Th17 functions (Figure 1 below) ²⁹.

Figure 1. CD8 regulatory cell expression (CD8+CD28- T cells, arrows) is subnormal in MS (second panel) compared to healthy controls (first panel), however this low expression can be up-regulated with immune modulator (third panel).

We also illustrate our capabilities for measuring gene expression (Figure 2) and serum

yet still had markedly suppressed RNA expression for 5,000 differentially-expressed genes compared to therapy-naïve exacerbations in right panel. x-axis = fold down (to L) or up (to R); y-axis = significance

Figure 3. Multiplex analysis of proteins expressed by activated MNC. Cells were exposed to media only or to an agent that affects MS exacerbations and progression, then activated for 48 hours. Supernatants were analyzed for Th1, Th17, Th2, IFN-stimulated genes, and adhesion molecules (shown here), in addition to monokines, B cell factors, and neuroprotective proteins (dns). Columns are different patient and control groups, row are heat maps of average expression. Red = increased expression vs. media control; Blue = decreased expression vs. control; hue = statistical significance, with more saturation having lower p values (more zeros).

2.2 The hypothesis is that ACTHAR treatment in MS relapses generates a tolerogenic immune environment that suppresses inflammation and facilitates brain repair. We've found that CD8+CD28- suppressor cells are low in MS and are upregulated by several classes of immune modulators. The tolerogenic immune environment will be assessed in 18 ACTHAR-treated MS patients.

2.3 Overall objective is to determine Treg expression and neuroprotection signature, as well as identify gene and immune protein signatures in ACTH-treated MS:

2.4 Specific aims and experiment design with serum, MNC, and RNA samples from baseline, last day of ACTHAR (day 10 of therapy), 1 month post 1st dose, and months 3 and 6:

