- 1. **Aim1**. Determine immune subset expression in CD4+FOXP3 Tregs and CD8+CD28- T suppressor cells by flow cytometry at each visit above.
- 2. **Aim 2**. Determine global gene expression profiling in MNC with 913,000 probes at each visit above. Bioinformatics will include pathway analysis and ACTHAR-induced RNA signature.
- 3. **Aim 3**. Determine serum protein profiling for immune-regulated cytokines (Th1, Th2, Th17, monokines...) and neuroprotective proteins (NGF, BDNF, ACTH, HGF, CNTF, IL-10...) at each visit above.

4. **Aim 4.** All data from protein and gene expression, as well as immune subset expression will be compared to our database generated from therapy-naïve stable and exacerbating MS. ACTHAR signature will analyzed based on these comparisons.

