2.5 Methods

Blood is drawn from 18 MS patients at baseline, last day of ACTHAR (day 10 of therapy), 1 month post 1st dose, and months 3 and 6. Mononuclear cells (MNCs) from four 8cc heparin green-top tubes (40-60 million cells) are separated on Ficoll-Paque gradients. 30M cells are needed for flow cytometry. 20M cells are needed for total RNA preparation.

Specific Aim 1. Determination of ACTHAR effects on immune cell subsets in relapsing remitting MS (RRMS), emphasizing expression on CD8 cells including the CD8+CD28-regulatory subset. Flow cytometry will be conducted to determine the effect of ACTHAR on in vivo expression of surface markers on T cells (CD4, CD8, CD28, FOXP3). Reagents are from e-Biosciences and B-D. (MAbs = CD4, CD8, CD28, CD27, CD25, FOXP3).

Specific Aim 2. Global gene expression profiling in MNC will be measured with 913,000 probes at each sample. Bioinformatics will include pathway analysis and ACTHAR-induced RNA signature. Total RNA will be isolated from 20M cells, as the template for synthesizing cDNA for gene expression array analysis with Affy HTA kit. RT-PCR will be performed for validation of specific gene signatures.

Specific Aim 3. Serum from each sample will be applied on Procarta multiplex assay plates according to manufacturer's instruction. Immune, neuroprotection, and other proteins will be measured with 40 highly-selected targeted antibodies for Th1, Th2, Th17, monocyte, neuroprotection, cell proliferation and death, and adhesion molecule panels.

Specific Aim 4. Advanced bioinformatics with Gene Set Variation Analysis:

- 1. Identify differential gene expression (DEG) between groups;
- 2. Analyze pathways by Ingenuity Pathway Analysis (IPA);
- 3. Discover transcriptional signature of genes and gene pathways;

4. Build a predictive model using machine learning algorithms including Random Forests (RFs) and Support Vector Machines (SVMs).

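### The RNA signature comes from bulk mononuclear-cell RNA with no account of cell mix, so part of it can reflect changed cell proportions and not regulation within cells

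*Combined protocol and SAP*

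**What the plan says.** All references are to the combined protocol and SAP.

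- **Cell preparation (2.5).** "Mononuclear cells (MNCs) from four 8cc heparin green-top tubes (40-60 million cells) are separated on Ficoll-Paque gradients". No sorting into T cells, B cells, NK cells or monocytes is described.
- **RNA source (2.5, Specific Aim 2).** "Total RNA will be isolated from 20M cells, as the template for synthesizing cDNA for gene expression array analysis with Affy HTA kit". On scope: "Global gene expression profiling in MNC will be measured with 913,000 probes at each sample".
- **Expression analysis (2.4 and 2.5).** "Bioinformatics will include pathway analysis and ACTHAR-induced RNA signature". Specific Aim 4 begins with "Identify differential gene expression (DEG) between groups" and goes on to pathway analysis, a transcriptional signature and machine-learning models, under a Gene Set Variation Analysis heading. The only validation named is this: "RT-PCR will be performed for validation of specific gene signatures".
- **Flow cytometry (2.5, Specific Aim 1).** The listed antibodies are CD4, CD8, CD28, CD27, CD25 and FOXP3. On cell needs: "30M cells are needed for flow cytometry. 20M cells are needed for total RNA preparation".
- **Expected change in cells (2.1, on CD8+CD28- cells).** "Some MS immune modulators can elevate numbers of this subpopulation". Section 2.2 repeats this observation alongside its hypothesis.
- **Statistical model (3.4).** A mixed effects model for longitudinal data, tests at 0.05, no covariates listed.
- **Intended use (2.6).** Better understanding of mechanism of action, and possible biomarkers.

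**The concern.** MNC are a mixture. The bulk signal for a gene is the sum over cell types of each type's share times its expression. If a subset's share changes between visits, genes enriched in that subset change in bulk even when no cell alters its expression. Those changes then pass into the differential expression, pathway and signature steps and can be read as regulation.

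The plan gives its own reason to expect such a change, at least for CD8+CD28- cells, and it measures T-cell subsets on the same draws. Yet it never links the flow results to the RNA results: Aim 4 only compares each data type with an external database. RT-PCR on the same bulk RNA would confirm the array signal but could not separate composition from regulation.

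At stake is the mechanistic interpretation. Where a measured T-cell subset drives the signal, Aims 1 and 2 could also be presented as separate lines of evidence when they share one source.

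**Working it through.** The documents state no power, SD, effect size or cell share, so there is no figure to reproduce. What follows is an illustration.

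**Inputs from the documents:** 18 patients (3.1a); 0.05 level (3.4; sidedness not stated, two-sided assumed); bulk RNA from 20M MNC, yield 40-60M, 30M needed for flow (2.5).

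**Inputs assumed:** subset share before (p0) and after (p1); expression in the subset relative to other cells (r); SD of the within-patient log2 change.

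**Step 1. Apparent fold change with zero regulation**

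FC = [1 + p1(r - 1)] / [1 + p0(r - 1)], which tends to p1/p0 for a gene exclusive to the subset.

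With p0 = 0.15 and p1 = 0.20:

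- exclusive: 0.20/0.15 = 1.33, log2 0.415
- r = 20: 4.80/3.85 = 1.25, log2 0.318
- r = 10: 2.80/2.35 = 1.19, log2 0.253
- r = 5: 1.80/1.60 = 1.125, log2 0.170

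**Step 2. Chance of a significant paired t-test**

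Noncentrality = log2 FC × √18 / SD, with 17 degrees of freedom and a critical value of 2.11. At SD 0.6 the exclusive gene has 0.415 × 4.243 / 0.6 = 2.93.

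| Gene | SD 0.4 | SD 0.6 | SD 0.8 |
|---|---|---|---|
| Exclusive | 0.985 | 0.79 | 0.55 |
| r = 20 | 0.89 | 0.56 | 0.36 |
| r = 10 | 0.72 | 0.39 | 0.24 |
| r = 5 | 0.40 | 0.21 | 0.14 |

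At an assumed per-gene threshold of 0.001, the exclusive gene at SD 0.6 falls from 0.79 to 0.21.

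**Step 3. Other shifts (SD 0.5, level 0.05)**

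- 5% to 7.5%: 0.15 (r = 5) and 0.71 (r = 20)
- 10% to 20%: 0.83 (r = 5) and 1.00 (r = 20)

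A small shift in a modestly enriched gene usually goes undetected. A larger shift in a strongly enriched gene is found almost every time.

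**Step 4. Does adjustment help?**

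Simulation of 4,000 runs per case with n = 18, zero regulation, residual SD 0.4, and between-patient SD of the share 0.03 before and 0.04 after. The adjusted analysis regresses the log2 change on the change in share and tests the intercept.

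| Shift | r | Unadjusted | Adjusted |
|---|---|---|---|
| none (10%) | 5 / 20 | 0.05 / 0.05 | 0.04 / 0.05 |
| 10% to 15% | 5 / 20 | 0.40 / 0.81 | 0.05 / 0.04 |
| 10% to 20% | 5 / 20 | 0.92 / 1.00 | 0.04 / 0.05 |

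The share is taken as known without error here. Estimated shares would correct less completely.

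**Step 5. What flow cytometry can supply**

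The listed panel has T-cell markers only, so it gives no direct share for monocytes, B cells or NK cells. Flow and RNA together need 30M + 20M = 50M cells. A 40M draw is 10M short, so some draws may lack full flow or RNA data.

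**The case against.** The strongest case on the other side has four parts.

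1. **A composition effect may be part of the treatment effect.** Cell mix is measured after treatment starts, and section 2.2 hypothesises a changed immune environment. A signature driven by composition is still a change associated with ACTHAR and may be a usable biomarker. This stands. It is why the adjusted result should sit beside the unadjusted one and not replace it.
2. **The documents predict little about cell mix.** A reader might infer that Aim 1 expects shifts across the mixture. It does not: Aim 1 only sets out to determine CD4+FOXP3 and CD8+CD28- expression. The only rise described is in CD8+CD28- cells (2.1 and 2.2), as an effect of other immune modulators on which the hypothesis draws. No shift in monocytes, B cells or NK cells is predicted. This stands.
3. **The effect is not certain for any given gene.** A reader might infer that a cell shift will be reported as regulation. The working supports only that it can be. A bulk change proportional to the shift holds only for subset-exclusive genes, and multiplicity control would reduce detections further. This stands too.
4. **The study is small and exploratory.** It has one arm and 18 patients, the mechanism claim is hedged, and the analysis outline is brief; silence is not a decision against adjustment. That limits the weight of the point. It does not remove it, because following the plan as written leaves the two explanations unseparated.

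**Conclusion.** The concern holds in a limited form. The plan derives its RNA signature from bulk MNC RNA, names no step that accounts for cell mix, and itself gives reason to expect a change in one subset. Part of the signature can therefore be compositional, which weakens the within-cell mechanism and pathway reading and leaves its use as a biomarker intact.

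The size depends on the shift, the enrichment of the gene, the SD and the threshold. In the main illustration, the chance that a gene with no regulation is declared changed runs from 0.21 (5-fold enriched) to 0.79 (subset-exclusive). Every share, enrichment ratio and SD behind these figures is assumed.

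A reader might also conclude that the signature merely repeats what Aim 1 has already measured. The documents do not support that in general: with a T-cell-only panel, a shift in monocytes, B cells or NK cells would not show directly in the Aim 1 data.

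**What to change.** Add to section 2.5 (Specific Aims 2 and 4) and section 3.4:

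- Keep the unadjusted signature as the description of change in MNC, usable as a candidate biomarker.
- Beside it, prespecify a composition-adjusted analysis. Use array-based deconvolution estimates for monocyte, B-cell and NK-cell shares, plus the flow-measured T-cell subset shares from the same draw where available. State what is used when a draw yields too few cells for both assays.
- Report both gene lists and both sets of pathway results. Base claims of within-cell regulation and pathway mechanism only on genes that persist after adjustment.

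This needs no new samples or visits, only SAP text and analysis code. The price is a few degrees of freedom out of at most 18 × 5 = 90 samples, error in the deconvolution estimates (so some composition effect may remain), and probably a shorter list of genes supporting mechanism claims.

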2.6 Outcomes

This data may lead to better understanding of the mechanism of action of ACTHAR and identifying signatures/biomarkers in ACTHAR-treated MS. In addition, MRI, CD8+CD28- cell numbers, serum proteins, and RNA may be biomarkers for efficacy.

Part III. Patient criteria and publications

3.1a Inclusion Criteria

This study will be restricted to adult patients (>18 years) undergoing a clinical relapse who also must have a contrast-enhancing CNS lesion, either clinically or non-clinically relevant. Sample size under consideration is 18 patients. The population on which analyses will be conducted consists of all patients who have received at least 1 dose of study medication and for whom at least two time-points (baseline and at least one additional time-point) for MRI data are available (Intent-to-treat analysis).

3.1b Exclusion Criteria

1-Patients will be excluded if they only have a clinical relapse which is not associated with MRI findings of a new or enlarging MS lesion.

2-Patient will be excluded if they cannot give written consent

3-Patients will be excluded if they have an active infection

4-Patients will be excluded if they already received steroids (IV or oral) within last 30 days of receiving ACTHAR

5-Pregnant or lactating patients will be excluded from this study.

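### Specific Aim 4 lists gene selection before an RF/SVM model and plans no validation; run in that order on the same data, the model can look near-perfect on pure noise

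*Combined protocol and SAP*

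**What the plan says.** Section 2.5 gives the data: "Blood is drawn from 18 MS patients at baseline, last day of ACTHAR (day 10 of therapy), 1 month post 1st dose", and at months 3 and 6. That is five visits, so at most 18 × 5 = 90 samples from 18 independent patients. Under Specific Aim 2, "Global gene expression profiling in MNC will be measured with 913,000 probes at each sample". Section 3.1a gives the sample size without derivation ("Sample size under consideration is 18 patients"), and section 3.5 does not replace patients who withdraw after treatment, so 18 is an upper limit.

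Specific Aim 4 in section 2.5, headed as Gene Set Variation Analysis, is a numbered list. Step 1 is "Identify differential gene expression (DEG) between groups", step 2 is pathway analysis, step 3 is "Discover transcriptional signature of genes and gene pathways", and step 4 is "Build a predictive model using machine learning algorithms including Random Forests (RFs) and Support Vector Machines (SVMs". Section 2.4, Aim 4 adds comparison data: "All data from protein and gene expression, as well as immune subset expression will be compared to our database generated from" therapy-naive stable and exacerbating MS. The size of that database is not given.

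The only validation mentioned for the gene work is in Specific Aim 2: "RT-PCR will be performed for validation of specific gene signatures". Section 3.4 covers summary statistics, mixed effects models, the 0.05 level and Pearson correlation. It does not mention the predictive model.

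**The concern.** When genes are chosen because they separate the groups in all samples, every sample has already influenced the feature set. Cross-validating only the classifier afterwards does not test it on unseen data. With hundreds of thousands of probes and 18 patients, some probes will separate any two groups by chance, and the classifier will then appear to predict well.

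This is separate from multiplicity control of the gene list. A corrected list still leaks if it was chosen on the samples used to assess the model.

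The repeated visits raise a second problem. If folds are formed by sample, the same patient can be in both training and test data.

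At stake is whether any accuracy reported for an ACTHAR signature could be interpreted. The primary MRI outcome is not affected.

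**Working it through.** The plan states no accuracy, power or precision figure for the model, so there is nothing to reproduce. The check is a simulation on Gaussian noise, where true accuracy is 0.5.

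**Inputs from the documents:** 18 patients, five visits, 913,000 probes, RF and SVM as algorithms, selection listed before modelling.

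**Assumed:** class split, number of genes kept (k), database size, within-patient correlation, and independent features. Most runs used 20,000 features to save time.

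**Check 1: where selection takes place.** Features were ranked by |mean₁ − mean₀| / √(s₁²/n₁ + s₀²/n₀) and the top k kept, either once on all data (outside) or again in each training fold (inside). A linear SVM or a 200-tree RF was then cross-validated.

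| Setting (pure noise) | Outside | Inside |
|---|---|---|
| 9 v 9, SVM, k = 10 to 200 | 0.997 to 1.00 | 0.50 to 0.57 |
| 9 v 9, RF, k = 10 | 0.98 | 0.52 |
| 9 v 9, RF, k = 50 | 1.00 | 0.48 |
| 6 v 12, SVM, k = 50 | 1.00 | 0.49 |
| 9 v 9, all 913,000 features, SVM, k = 50 (2 data sets) | 1.00 | 0.56 |
| 18 patients pre v post, correlation 0.5, whole patients left out, SVM, k = 50 | 0.997 | 0.51 |
| Same, RF | 0.94 | 0.45 |
| 18 v database of 20, SVM, k = 50 | 1.00 | 0.51 |
| 18 v database of 50, SVM, k = 50 | 0.99 | 0.47 |
| 18 v database of 100, SVM, k = 50 | 0.98 | 0.48 |

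The 6 v 12 and database rows are balanced accuracy. The pre v post rows show that leaving out whole patients does not help if selection has already used them.

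For scale, in a genuine independent test of 18 balanced cases, the chance of 17 or more correct under the null is (18 + 1)/2¹⁸ = 19/262,144 = 0.00007. The outside scheme reaches that level routinely on noise.

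**Check 2: splitting by sample or by patient.** These runs used 18 patients × 5 visits, 20,000 null features, a random 9/9 label constant within patient, a ridge classifier, and selection correctly repeated inside each fold.

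| Within-patient correlation | 10-fold by sample | Whole patients left out |
|---|---|---|
| 0.2 | 0.92 | 0.51 |
| 0.4 | 0.99 | 0.53 |
| 0.6 | 1.00 | 0.48 |

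The direction depends on the label. With a baseline v day-10 label (correlation 0.6, 5,000 features, no gene selection), 10-fold by sample gave 0.05, while leaving out whole patients gave 0.54. A further null run with a visit label split by sample gave 0.12. The held-out sample resembles the same patient's other sample, which is in the training set with the opposite label.

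**Check 3: a side effect of leaving out one patient.** With a 9/9 patient-level label, removing one patient leaves 8 v 9, so the held-out patient always belongs to the smaller training class. In the run without gene selection this gave 0.07, again on noise. Folds must therefore keep the classes balanced.

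**Check 4: precision once validation is sound.** The exact 95% interval for 14/18 correct is 0.52 to 0.94, and for 9/18 it is 0.26 to 0.74.

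**The case against.** A reader might infer that the plan commits to selecting genes on the same 18 patients and feeding them to the model, so that its accuracy is bound to be spurious. The documents do not say this.

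- **Inputs.** Aim 4 lists tasks. It does not state that the differentially expressed genes are the RF/SVM inputs. The Gene Set Variation Analysis heading suggests that gene-set scores might be used. This stands. The same leak would arise if gene sets were chosen by comparing groups on all samples, but that variant was not simulated.
- **Patients.** The groups are undefined, and section 2.4 brings in a database of other patients. This also stands, so the 18 cannot be assumed to be the only data. It does not remove the risk: accuracy on noise stayed at 0.98 to 1.00 with 20 to 100 assumed database patients.
- **Repeated visits.** A reader might infer that splitting by sample always inflates accuracy. It does so for a label constant within patient. For a visit label it pushes accuracy far below chance.
- **RT-PCR.** This might be taken as validation of the model. The plan describes it as checking specific gene signatures and does not describe a test of the model on new patients.
- **Stakes.** No accuracy target, decision rule or primary outcome rests on the model. Section 2.6 says only that the data may identify biomarkers, and it does not mention the model. This limits the severity. However, section 2.3 puts identifying gene signatures in the overall objective, and the Supplement labels the oxygen extraction work exploratory while nothing gives this model that label.

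**Conclusion.** The concern holds as a conditional one. The plan defines no outcome, inputs, training samples or validation for the model, and lists the steps in an order that gives a wrong answer if followed on the data used for assessment. In that case accuracy under the null is about 0.94 to 1.00, against 0.45 to 0.57 when selection is inside the folds. Splitting by sample is a second source of bias, with a direction that depends on the label.

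The sizes rest on the assumptions stated above. Real probes are correlated, so the effective number of features is below 913,000, but 20,000 were already enough to produce the result.

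Confidence is high that validation is missing. It is moderate that leakage would occur, since the plan leaves the workflow open. This should be corrected before the model is built, but it does not threaten the MRI analyses.

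**What to change.** Add the following to Specific Aim 4 or section 3.4:

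1. State what the model predicts, which groups and visits it uses, and whether database samples enter training, testing or both.
2. Repeat differential expression selection, pathway scoring and tuning inside each training fold.
3. Form folds from whole patients with all their visits, and keep the classes balanced within folds.
4. Report accuracy with a patient-level interval (for example a patient-level bootstrap) and a permutation test that reruns the whole pipeline.
5. Label the model hypothesis-generating until it has been tested in independent patients.

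The cost is SAP text and computing time, with no new patients or samples. The downside is a lower accuracy figure with a wide interval, as the 14/18 example shows.

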2.6 Outcomes

This data may lead to better understanding of the mechanism of action of ACTHAR and identifying signatures/biomarkers in ACTHAR-treated MS. In addition, MRI, CD8+CD28- cell numbers, serum proteins, and RNA may be biomarkers for efficacy.

Part III. Patient criteria and publications

3.1a Inclusion Criteria

This study will be restricted to adult patients (>18 years) undergoing a clinical relapse who also must have a contrast-enhancing CNS lesion, either clinically or non-clinically relevant. Sample size under consideration is 18 patients. The population on which analyses will be conducted consists of all patients who have received at least 1 dose of study medication and for whom at least two time-points (baseline and at least one additional time-point) for MRI data are available (Intent-to-treat analysis).

3.1b Exclusion Criteria

1-Patients will be excluded if they only have a clinical relapse which is not associated with MRI findings of a new or enlarging MS lesion.

2-Patient will be excluded if they cannot give written consent

3-Patients will be excluded if they have an active infection

4-Patients will be excluded if they already received steroids (IV or oral) within last 30 days of receiving ACTHAR

5-Pregnant or lactating patients will be excluded from this study.

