1.3 MRI Assessments

All images will be performed at the University of Chicago's Magnetic Resonance Imaging Research Center (MRIRC). The MRIRC is fully dedicated to MRI research and located in the Q300 suite in the Department of Radiology of the University of Chicago Medical Center. The MRIRC houses two state of the art MRI scanners and is staffed by 2 full-time MRI technologists, research nurses, and coordinators. [name] has over 20 years' experience in neurological imaging and is the Director of Neuroimaging for the MRIRC and will oversee all aspects of imaging.

The primary outcome of all MRI techniques is to determine whether there is an improvement and subsequent stabilization/repair over time of tissue damage caused by inflammatory MS disease activity. Multiple conventional and nonconventional MR imaging modalities are examined here to determine which of these are the most sensitive and reliable in detecting microstructural damage and repair over time. The results of this study will also greatly impact the design of future MS trials by providing a guide for selecting the most appropriate MRI and immune methods to assess treatment efficacy in MS.

Conventional MRI

Quantitative T1 Gd+, T2, T1 chronic, and BPF analysis:

Commonly used MRI metrics in most studies include a post-contrast T1 weighted sequence and a T2 weighted sequence. These are useful for detecting new inflammatory lesions. The contrast-enhancing lesions are transient (less than 2 months on average) and are indicative of active lesions. The T2 lesions are more permanent and are thought to develop after enhancement ceases. Measurement of lesion load in terms of number and volume, both active and inactive (T1 Gd+, T2 chronic lesions, and T1 chronic lesions) will be examined over time.

Specific Aim: determine the effects of ACTHAR in improving the characteristics of contrast enhancing lesions (T1 Gd+) observed at baseline and followed squentially over time to the development of T2 and chronic T1 signal intensities.

Quantitative nonconventional MRIs (see Supplement for protocol details):

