3.4 Statistical Analysis

All data collected will be documented using summary tables, figures, and patient data listings. For longitudinal data, mixed effects regression model will be used to summarize patterns over the one-year period. All hypothesis testing will be at the 0.05 level of significance. Correlation analyses between specific measures will be accomplished using Pearson's correlation co-efficient.

All summary statistics will be displayed as a function of study visit or assessment time. Summary statistics for continuous variables will include n, mean, standard deviation, minimum, median, and maximum. For categorical variables, frequencies and percentages will be presented. Graphical displays will be provided as appropriate.

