Whole brain isotropic voxel size mcDESPOT imaging will be acquired using the following imaging parameters: FOV = 22 cm, matrix = 128 × 128, slice thickness = 2 mm; SPGR parameters: echo time/repetition time (TE/TR) = 2.1/6.7 ms, flip angle (α)=[3,4, 5, 6, 7, 8, 11, 13, 18]°; bSSFP parameters: TE/TR = 1.8/3.6 ms, α = [11, 14, 20, 24, 28, 34, 41, 51, 67]°, two phase cycles acquired per bSSFP flip angle. The total mcDESPOT acquisition time is ~13 min ¹³.

Magnetization transfer imaging (MTI): this imaging technique interrogates the transfer of magnetization (MT) from protons bound to macromolecules to more mobile water associated protons. This MT effect is quantified by acquiring two images, one with and the other without a resonance pulse. MTI will be performed using 2D gradient echo (GE) sequence (TR=640, TE=12, FA 20°) with and without an off resonance radiofrequency (RF) saturation pulse (off frequency=1.5 kHz, Gaussian envelope duration 7.68ms, FA=500°).

MTR=(Moff - Mon)/Moff.

MTR of the active and inactive lesions as well as normal appearing white and gray matter will be determined. MTR of the lesions will be determined by the region of interest (ROI) analysis.

Diffusion Tensor Imaging (DTI): images will be acquired using single shot spin-echo planar pulse sequence TR= 7658 ms, TE= 70 ms, matrix size = 128 x 128, FOV = 224 x 224 with diffusion gradients (b-value =800 s/mm²) applied in 32 noncollinear directions. Fractional Anisotropy, mean diffusivity, radial ($\lambda \perp$) and axial (λ II) diffusivities of active and chronic lesions will be determined by ROI analysis.

References:

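### Section 3.1a admits a patient whose only enhancing lesion is in the spinal cord, and that patient supplies no data to the active-lesion MRI aims.

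*Combined protocol and SAP*

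**What the plan says.** **Entry.** Section 3.1a requires that a patient in clinical relapse "must have a contrast-enhancing CNS lesion, either clinically or non-clinically relevant". Exclusion 1 in section 3.1b removes patients whose relapse is "not associated with MRI findings of a new or enlarging MS lesion". Neither rule names a site within the CNS.

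**Analysis population.** Section 3.1a takes patients with at least one dose for whom "at least two time-points (baseline and at least one additional time-point) for MRI data are available". It does not ask for an active lesion in the imaged region.

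**Sample size.** "Sample size under consideration is 18 patients", with no effect size, SD or power attached. Section 3.4 adds only that "All hypothesis testing will be at the 0.05 level of significance".

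**Aims.** The conventional MRI aim in section 1.3 is to "determine the effects of ACTHAR in improving the characteristics of contrast enhancing lesions (T1 Gd+) observed at baseline" and to follow those lesions over time. The perfusion and Ktrans aims are also set in active lesions. The MWF, MTR and DTI aims each cover active (Gd+) and inactive T2 lesions.

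**Imaging.** The supplement specifies "Whole brain isotropic voxel size mcDESPOT imaging" and describes perfusion as cerebral. It contains no spinal cord sequence, and cord lesions are mentioned nowhere in the document.

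**The concern.** The entry rule is wider than what the imaging can measure. A patient whose only enhancing lesion lies in the cord meets 3.1a. The patient also passes exclusion 1 if that lesion is new or enlarging, and joins the analysis population once a baseline and one later MRI exist. Brain imaging then shows no active lesion to follow.

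In a study of about 18 patients, each such place weakens the analyses set in active lesions. The plan does not say how this patient is handled in those analyses, which scan establishes eligibility, or how many patients each endpoint will rest on.

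**Working it through.** **Step 1. Compare each aim with what a cord-only patient can supply.** The sources are section 1.3, Part II and the MRI supplement.

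| Measure | Lesions the aim needs | Region identified from | Cord-only patient supplies |
|---|---|---|---|
| Conventional Gd+ follow-up | Enhancing at baseline | Brain (grouped with BPF) | Nothing |
| Perfusion (CBF, MTT) | Active | Cerebral, named | Nothing |
| Ktrans | Active | Rationale refers to brain; acquisition names no region | Nothing |
| MWF (mcDESPOT) | Active and inactive T2 | Whole brain, named | Inactive half only |
| MTR | Active and inactive T2 | Not named | Inactive half only |
| DTI | Active and inactive T2 | Not named | Inactive half only |
| Quantitative T1 | T1 lesion characteristics, not only active | Brain reference tissues | Data, if brain lesions are present |
| T2 and chronic T1 load, BPF | No enhancing lesion needed | Brain | Data |
| OEF | Patient before and after treatment | Brain (rationale) | Data |
| Immune assays | None | Blood | All time-points |

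Three aims lose the patient entirely and three lose the active-lesion half. The rest are unaffected.

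**Step 2. Expected number affected.** The plan's 18 cannot be reproduced, because no power calculation is given. The cord-only share p is not in the documents, so it is assumed. The expected count is 18p, and the chance of at least one such patient is 1 − (1 − p)^18.

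| Assumed p | Expected of 18 | P(at least 1) | P(at least 2) |
|---|---|---|---|
| 2% | 0.36 | 0.305 | 0.050 |
| 5% | 0.90 | 0.603 | 0.226 |
| 10% | 1.80 | 0.850 | 0.550 |
| 20% | 3.60 | 0.982 | 0.901 |

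**Step 3. Detectable change, as an illustration.** Assume one change score per patient and a one-sample (paired) t-test, two-sided 0.05, 80% power. The two-sided test and the 80% are assumptions; only the 0.05 is in the plan. Power is the probability that a noncentral t variable with n − 1 degrees of freedom and noncentrality d√n exceeds the 97.5% point of central t. Solving for d at 80% power gives the third column. The last column holds d at 0.701 and lets n fall.

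| Patients lost | n | Detectable d (SD) | Power at d = 0.701 |
|---|---|---|---|
| 0 | 18 | 0.701 | 0.800 |
| 1 | 17 | 0.724 | 0.774 |
| 2 | 16 | 0.749 | 0.745 |
| 3 | 15 | 0.778 | 0.714 |
| 4 | 14 | 0.810 | 0.679 |

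Rounding the expected counts, 10% corresponds to n = 16 and 20% to n = 14. At 2% to 5% the loss is none or one patient.

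**Step 4. Coverage within the brain.** Ktrans uses 4 slices of 8 mm: 4 × 8 = 32 mm. Perfusion, read as 15 slices of 3 mm, covers 15 × 3 = 45 mm if contiguous. Slab placement is not specified. An enhancing brain lesion could therefore still lie outside one or both slabs.

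**The case against.** The strongest reply is that the affected group may be very small. Section 3.1a accepts a lesion whether or not it explains the symptoms, so a patient with a cord relapse and a silent enhancing brain lesion still supplies active-lesion data. Section 1.1 says new MRI activity can outnumber relapses 10:1, though it gives no site. If the baseline study scan also decides eligibility and covers only the brain, a cord-only patient could not qualify at all. These points limit the size. They do not close the gap, because the documents do not say which scan establishes eligibility and the written criterion remains any CNS lesion.

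It can also be said that brain-only imaging is partly inferred. That is correct: the Ktrans, MTI and DTI acquisition descriptions name no region. Nothing in the documents contradicts the inference, and no cord acquisition is provided.

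A third reply is that section 3.4 plans mixed effects regression, not a paired t-test, and that no target effect is stated. That stands, so the SD figures are illustrative only. A mixed model still cannot supply a series for an active lesion that was never imaged.

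Three stronger readings are tempting but not supported:

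- A reader might infer that these places can never be refilled. Section 3.5 rules out replacement only for patients who withdraw after drug treatment and is silent on patients without an evaluable lesion.
- A reader might infer that 18 is not the sample for the main MRI aims. The primary MRI outcome in section 1.3 concerns improvement and repair of inflammatory tissue damage generally, and several aims include inactive lesions or need no lesion.
- A reader might see a contradiction between the enhancing criterion in 3.1a and the new-or-enlarging criterion in exclusion 1. Both can apply to the same patient.

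**Conclusion.** The point holds as a mismatch between eligibility and imaging coverage. It affects the conventional Gd+, perfusion and Ktrans aims and the active-lesion half of the MWF, MTR and DTI aims. A cord-only patient is not lost to the study.

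Its size cannot be fixed from the documents. Over an assumed share of 2% to 20%, between 0.4 and 3.6 of 18 patients are expected to be affected. On the illustrative calculation the detectable change rises from 0.70 SD to at most about 0.81 SD. This is a modest loss, and it can be avoided by a one-line change. The conclusion rests on reading CNS to include the cord, and on the inference that the sequences with no named region are brain scans.

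**What to change.** Change section 3.1a to require at least one contrast-enhancing brain lesion, clinically relevant or not, on the baseline MRI before the first dose. This also settles which scan establishes eligibility.

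For each endpoint, report the number of patients with an evaluable active lesion. This is needed even after the eligibility change, because the 32 mm Ktrans slab and the 45 mm perfusion slab may miss some brain lesions.

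The cost is one line in 3.1a and one reporting statement in 3.4. Recruitment would be somewhat slower, because relapses with only a cord lesion would no longer qualify. The baseline scan would also have to be read before dosing, and the overview has patients start within 48 hours of relapse assessment.
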